#### **13.1.4.3. Infusion-Related Reaction**

Infusion-related reactions are checked in the eCRF and will be presented in listings.

Treatment emergent classed as infusion-related reaction will be summarized for the safety population, safety – 2nd treatment course in Main Study Period subset and safety – Extension Study Period subset for each treatment course, by relationship, intensity, SOC and PT displaying the number and percentage of patients with at least one TEAE using only the most severe TEAE recorded at each level of summarization. The total number of events and number of patients with at least one treatment-emergent classed as infusion-related reaction will also be displayed.

Number of patients with at least one TEAE classed as infusion-related reaction by ADA status tagged with CT-P10 will be summarized. For summary of IRR at first, second course of treatment in Main Study Period, Patients who have ‘Positive’ ADA result at Week 24 and Patients who have at least one ‘Positive’ ADA result in Week 24 and Week 48 will be defined as positive, respectively. For summary of IRR at treatment course of Extension Study Period, Patients who have at least one ‘Positive’ ADA result in Week 24, Week 48 and Extension Week 24 will be defined as positive.

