**Figure 2: Schematic Diagram of Study Patients for the Main Study Period (up to Week 48)**

The Extension Study Period is designed to evaluate additional safety and immunogenicity.

Patients can continue to the Extension Study Period with an additional course of treatment regardless of the number of treatment courses they were treated with during the Main Study Period if the following conditions are met:

- Complete all of the scheduled visits up to Week 48 and
- Meet the predefined safety criteria.

The third course of treatment should be initiated between Week 48 and Week 52. If administration of the third course of treatment is deemed necessary to be initiated after Week 52 at the discretion of the investigator, the study infusion can be administered within 72 Weeks from the first infusion of the first course of treatment after discussion with the sponsor. In this case, the study infusion must be initiated no later than 52 Weeks from Day 0 for the last enrolled patient.

[figure not shown]
Note that patients, who have the End-of-Study (EOS) visit at Week 48, can participate in the Extension Study Period if the patients sign an informed consent form within 24 weeks from the EOS visit and do not have prohibited medications prior to entering the Extension Study Period.

All patients eligible for Extension Phase from the Rituxan group will be randomized again in a 1:1 ratio to the CT-P10 or Rituxan group at Extension Week 0. The randomization will be conducted and stratified by:

- The number of courses they are treated during the Main Study Period and
- The European League Against Rheumatism (EULAR)-CRP response status (responder vs. non-responder) assessed at Week 40.

To keep the blind during the study, stratification factors will be entered for all patients at Extension Week 0. In the case there were no EULAR-CRP response status available at Week 40, the last EULAR-CRP response status assessment done between Weeks 40 and 48 will be used. Baseline values for assessment of EULAR-CRP will be the last value from screening to Day 0 (Week 0) of the study. A schematic of the study patient assignment for this randomization is presented in [Figure 3](#).

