### **13.7. Immunogenicity (Anti-drug antibodies and Neutralizing antibody)**

Blood samples for immunogenicity (ADA and NAb) assessment will be obtained at Week 0 Day 0, Week 24, Week 48, Extension Week 0, Extension Week 8, Extension Week 16, Extension Week 24 and EOS (if patient withdraws prior to study completion). Immunogenicity assessment consists of both ADA and NAb assay.

ADA assay will follow a three-tiered approach consisting of (i) a screening assay, (ii) specificity/confirmatory assay and (iii) titration. The test outcome for the screening assay will be: {'Potential Positive' or 'Negative'}. Samples that are 'Potential Positive' in the screening assay will be undergone further testing in the confirmatory (immunodepletion) assay to determine if patients are a true positive. The test outcome for the screening or specificity/confirmatory assay will be: {'Reactive', 'Negative' and 'N/A'}. 'Reactive' indicates a true positive test outcome and will be labeled as 'Positive' in outputs, 'Negative' is considered negative, and 'N/A' indicates the assay was negative at the screening phase of the process. Patients with a 'Negative' test outcome for either screening or specificity/confirmatory assay will be considered negative for the overall ADA assessment. For further characterization, the antibody level will be assessed by titration in confirmed positive samples.

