10. Additional vital signs including blood pressure, heart and respiratory rates, and body temperature (before administration [within 15 minutes prior to the beginning of the study drug infusion], within 15 minutes after the end of the study drug infusion, and at 1 hour [ $\pm 15$  minutes] after the end of the study drug infusion) will be assessed to monitor for possible hypersensitivity reactions. In addition, hypersensitivity should be monitored by routine continuous clinical monitoring including ECG (12-lead) monitoring 1 hour ( $\pm 15$  minutes) after the end of the study drug infusion. Emergency equipment and medication, such as adrenaline, antihistamines, corticosteroids, and respiratory support including inhalational therapy, oxygen, and artificial ventilator must be available.
11. ACR20, ACR50, ACR70, and hybrid ACR will be calculated from these assessments. It is recommended that the joint count assessments are performed by the same physician when possible.
12. Twenty eight tender and swollen joints, ESR or CRP, and patient's general health or global disease activity measured on VAS will be assessed for DAS28 calculation. The European League Against Rheumatism response criteria will be derived from the DAS28.
13. Patients with B-cell, IgM and IgG values below the LLN or less than 50% of their baseline value of Main Study Period should be monitored every 8 weeks ( $\pm 14$  days) after the study completion until recovery is achieved for one of them (equal to or higher than the lower limit of normal OR at least 50% of the baseline value of Main Study Period). Upon the study completion, additional follow-up of B-cell, IgM and IgG monitoring will be determined by the Data Safety Monitoring Board (DSMB).
14. Blood sampling for B-cell assessment at the first infusion date of the first course in Extension Study Period will be performed at predose (before administration [within 15 minutes prior to the beginning of the study drug infusion]), end of infusion (within 15 minutes after the end of the study drug infusion), and at 1 hour [ $\pm 15$  minutes] after the end of the study drug infusion.  
If Extension Week 0 is conducted on the same day with Week 48, the predose result from the B-cell samples obtained according to the scheduled schemes for Extension Week 0 will be the result of B-cell counts at Week 48.

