**\* IMPORTANT! For patients who receive the first course of treatment in Extension Study Period at Week 48, the samples should be obtained according to the sampling schemes for the Extension Week 0 Schedule. Otherwise, all scheduled samplings for Week 48 should be performed separately from the Extension Week 0 according to this sampling scheme.**

1. Predose: Blood samples will be obtained within 15 minutes prior to the beginning of the study drug infusion.
2. End of infusion: Blood samples will be obtained within 15 minutes after the end of study drug infusion.
3. 1 hour after end of infusion: Blood samples will be obtained 1 hour ( $\pm 15$  minutes) after the end of study drug infusion on dosing days.
4. Pretreatment: Blood samples will be obtained prior to the study drug infusion.
5. 24 hours after start of infusion: Blood samples will be obtained 24 hours ( $\pm 2$  hours) after the start of study drug infusion.
6. Time not specified: Blood samples will be obtained any time during the day.
7. The EOS Visit only needs to be completed if the patient withdraws prior to study completion. End-of-study assessments should be completed at least 8 weeks after the last study drug infusion and before Week 48 of Study Period if a patient withdraws prior to the completion of Week 48 visit. If the patient has completed by Week 48 of Study Period, an EOS Visit is not required.

**Sampling Times for Pharmacokinetic, Pharmacodynamic, and Safety Assessment for the Main Study Period between Weeks 24 and 48 (for patients who receive only first course of treatment)**

Study Period		PK	PD			Safety		
Week	Day		B-cell Kinetics	CRP, ESR	RF, anti-CCP	Immuno-globulin	Immuno-genicity	Hematology, Clinical Chemistry, Urine
24	168	Time not specified 	Time not specified 	Time not specified 	Time not specified 	Time not specified 	Time not specified 	Time not specified 
32	224	NA	Time not specified 	Time not specified 	NA	Time not specified 	NA	Time not specified 
40	280	NA	Time not specified 	Time not specified 	NA	Time not specified 	NA	Time not specified 
48	336	NA	Time not specified 	Time not specified 	Time not specified 	Time not specified 	Time not specified 	Time not specified 

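### The infusion-reaction-by-ADA table counts only some of the ADA samples collected, and for course 1 it relies on a single sample taken 154 to 168 days after the infusions

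*SAP*

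**What the plan says.** SAP 13.1 lists a table giving the proportion of patients with an infusion-related reaction by ADA status. SAP 13.1.4.3 defines that status course by course, using the assay with the CT-P10 tag.

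- **Course 1:** positive at Week 24.
- **Course 2:** at least one positive "ADA result in Week 24 and Week 48 will be defined as positive, respectively".
- **Extension course:** at least one positive "ADA result in Week 24, Week 48 and Extension Week 24 will be defined as positive".

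SAP 13.7 schedules immunogenicity samples at "Week 0 Day 0, Week 24, Week 48, Extension Week 0, Extension Week 8, Extension Week 16, Extension Week 24 and EOS", the last being for patients who withdraw. The sampling tables in SAP Appendix 1 place the Day 0 and Extension Day 0 samples before the infusion, and do the same at Week 24 for patients who receive course 2: "Pretreatment: Blood samples will be obtained prior to the study drug infusion".

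For patients whose third course starts on the Week 48 day, Appendix 1 says that "the samples should be obtained according to the sampling schemes for the Extension Week 0 Schedule". The footnotes to the Extension schedule then carry the Extension Week 0 pre-dose finding back to Week 48 for ECG and for B-cells (the pre-dose value "will be the result of B-cell counts at Week 48"). They contain no such statement for ADA.

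**The concern.** This is the table that links ADA to infusion reactions, and its list of visits is closed. SAP 13.7.1 and 13.7.3 summarise ADA and titer by visit, but they do not cross ADA with reactions, so they cannot make good what the list omits.

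Three consequences follow.

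1. In the Extension, which SAP 4.1 says is meant to evaluate further safety and immunogenicity, ADA seen only at Extension Week 0, 8 or 16 does not count.
2. For course 1, the only result used comes long after the reactions it is meant to explain. Protocol 1.2 says that serious reactions to the reference products were seen mainly in the initial course.
3. Exclusion from the positive group can depend on the outcome. Protocol 6.5.1 requires withdrawal after a life-threatening infusion-related anaphylactic reaction, and the ADA sample scheduled for a withdrawn patient is EOS, which the rule does not use.

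**Working it through.** The plan states no figure to reproduce. The check sets the rule in SAP 13.1.4.3 against the schedule in SAP 13.7 and Appendix 1, using nominal study days.

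**Visits counted**

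| Course | Scheduled up to end of course | Used | Omitted |
|---|---|---|---|
| 1 | Week 0, Week 24 (2) | Week 24 (1) | Week 0 |
| 2 | Week 0, Week 24, Week 48 (3) | Weeks 24, 48 (2) | Week 0 |
| Extension | Weeks 0, 24, 48; Extension Weeks 0, 8, 16, 24 (7) | Weeks 24, 48, Extension Week 24 (3) | Week 0; Extension Weeks 0, 8, 16 |

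EOS is not used for any course. If the third course starts on the Week 48 day, Week 48 and Extension Week 0 are one draw, leaving 7 − 1 = 6 draws. The rule then uses 3 of 6 if that draw counts as Week 48, and 2 of 6 if it is read literally as Extension Week 0.

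**Timing of the samples used**

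- Course 1, infusions on Days 0 and 14, Week 24 on Day 168: 168 − 0 = 168 and 168 − 14 = 154 days after. No pre-infusion sample is used.
- Course 2, infusions on Days 168 and 182: Week 24 is pre-dose on the first infusion day. Week 48 (Day 336) is 336 − 168 = 168 and 336 − 182 = 154 days after.
- Extension course, infusions on Extension Days 0 and 14: Weeks 24 and 48 precede it. Extension Week 24 is 168 and 154 days after.
- Week 48 to Extension Week 0: 0 to 52 − 48 = 4 weeks as planned. SAP 4.1 also allows a delay, in which "the study infusion can be administered within 72 Weeks from the first infusion of the first course of treatment", so the gap can reach 72 − 48 = 24 weeks.

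**Patients followed through the rule**

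- Extension patient, positive at Extension Week 8 only: not positive.
- Extension patient, positive at Extension Week 24 only, reaction on Extension Day 0: positive, although the antibody was first seen 168 days after the reaction.
- Course 1 reactor withdrawn before Week 24, EOS positive: not positive. The Week 0 result is not used either.
- Course 2 reactor withdrawn before Week 48: still classifiable from the Week 24 pre-dose sample, but a first positive at EOS is lost.

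**Illustration of the course 1 timing effect (all ADA inputs assumed)**

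Let p be pre-infusion ADA prevalence (5–10%), s later seroconversion among negatives (5–20%), q persistence of early positivity to the later sample (50–100%), and 2 the true relative risk by pre-infusion ADA. With r the risk in pre-infusion negatives, classifying by the later sample alone gives:

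- share positive: P = pq + (1 − p)s
- risk if positive: [pq·2r + (1 − p)s·r] / P
- risk if negative: [p(1 − q)·2r + (1 − p)(1 − s)·r] / (1 − P)

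The factor r cancels in the ratio, so the assumed overall reaction rate does not matter.

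- p = 0.10, s = 0.05, q = 1: P = 0.145. The ratio is [(0.20 + 0.045) / 0.145] / 1 = 1.69.
- p = 0.05, s = 0.20, q = 0.5: P = 0.215. The ratio is [(0.05 + 0.19) / 0.215] / [(0.05 + 0.76) / 0.785] = 1.116 / 1.032 = 1.08.

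Over the grid, a true relative risk of 2 appears as 1.08 to 1.69. This shows the direction of the effect under these assumptions; it does not estimate its size in this trial.

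**The case against.** The best defence is that the rule is a simple ever-positive-to-date definition built on a visit the SAP uses throughout. Week 24 also defines the antibody subsets in SAP 5.4 and the ADA-negative ANCOVAs. Prior rituximab is an exclusion (Protocol 4.1.2) and no ADA sample falls between Week 0 and Week 24, so Week 24 is the first scheduled result after exposure. No test or decision rests on the table, and ADA by visit, titers and reactions are all reported or listed elsewhere. Much of this stands. It makes the point one of completeness and labelling in a descriptive safety table, and it means a course 1 column by Week 0 ADA may hold few positives.

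Several stronger readings are tempting but unsupported:

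- *Pre-dose results are ignored.* Week 24 is the pre-dose sample for course 2, and Week 48 precedes a later-starting third course. The pre-dose visits left out are Week 0 and Extension Week 0.
- *All reactions are classified by ADA drawn afterwards.* That is wholly true only of course 1.
- *Withdrawn reactors have nothing but EOS.* Week 0 is scheduled for everyone, course 2 recipients also have Week 24, and Extension entry requires all visits to Week 48.

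It could also seem inconsistent to criticise late sampling and then ask for more post-infusion visits. These are two separate questions. An ever-positive class should use every sample; a separate pre-course class deals with the order of antibody and reaction.

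SAP Section 5 provides a Missing row in count tables where needed. SAP 13.1.4.3 does not say, however, when a patient without the named results is missing and when negative.

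**Conclusion.** The point holds in a limited form. Read literally, SAP 13.1.4.3 leaves out Week 0, Extension Weeks 0, 8 and 16, and EOS. Extension patients positive only at Extension Week 0, 8 or 16 are not counted as positive. Course 1 rests on one sample 154 to 168 days after the infusions, and a course 1 reactor withdrawn before Week 24 cannot be positive whatever EOS shows. Courses 2 and 3 mix pre- and post-infusion results. For patients dosed on the Week 48 day, the SAP does not say whether the sample just before the third course counts.

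A reader might infer that ADA status has been shown to be misclassified to a material degree. The documents do not support that: they give no ADA rates, so the number affected is unknown. The group withdrawn after a severe reaction is probably small. Applying the 0.5% serious-reaction rate in Protocol 1.2 to 361 patients gives 0.005 × 361 = 1.8, about 2 patients. That assumes the reference-product rate carries over, and it does not count withdrawals after non-serious reactions. No primary or secondary efficacy or PK conclusion is affected.

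**What to change.** Amend SAP 13.1.4.3 as follows, keeping the CT-P10-tagged assay and the descriptive status of the table.

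1. For each course, define ADA-positive as any positive result up to the end of that course, using every available sample, including Extension Weeks 0, 8 and 16 and EOS.
2. Add a column classifying patients by the last ADA result before the first infusion of that course: Week 0 for course 1; the Week 24 pre-dose sample for course 2; Extension Week 0 or, if that is missing, Week 48 for the Extension course.
3. State that when Extension Week 0 and Week 48 fall on the same day, the pre-dose Extension Week 0 ADA result is also the Week 48 result, matching the handling of ECG and B-cells.
4. Show patients with no ADA result for the classification in a separate missing category.

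All the samples are already scheduled, so the cost is SAP wording and programming for one extra column. The drawback is small cell counts, especially for pre-course positives in course 1, so the added column should be read as descriptive.

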### **13.2. Clinical Laboratory Evaluations**

Clinical laboratory safety tests will be performed and results will be converted to standard units which are provided by the central laboratory. Clinical laboratory tests (hematology, clinical chemistry, urinalysis, and immunoglobulins) will be summarized, by laboratory test type and treatment group, at each scheduled collection time for safety population and safety – Extension Study Period subset. For continuous parameters, change from baseline and actual value will also be summarized for all scheduled collection times after the first infusion.

The results for all non-numeric urinalysis parameters will be categorized into normal and abnormal using the central laboratory normal ranges provided prior to analysis and will be summarized in a shift table for the safety population and safety – Extension Study Period subset. The number and percentage of patients within each category will be displayed for baseline and for each post-baseline visit by parameters and treatment group.

All numeric parameters will be labeled with a CTCAE term and grading will be applied to post-baseline values for all numeric parameters where possible according to CTCAE v 4.0 [6]. Grades that require clinical input only will not be assigned to these parameters. Grades which are part numeric and part clinical input will be assigned based on the numeric portion only. The CTCAE terms and ranges for applicable parameters are listed in [APPENDIX 2: Table of CTCAE Terms and Grades](#) of this document. The CTCAE grades for this analysis will be Grade 1 (Mild), Grade 2 (Moderate), Grade 3 (Severe) and Grade 4 (Life-threatening). The CTCAE Grade 5 (Death) will not be applied in this analysis since death cannot be determined from a numeric laboratory result. If the post-baseline result for a patient does not satisfy any CTCAE grade, it will be classified as “No Grade”.

The number and percentage of patients with a result for each grade will be summarized by CTCAE term, visit, and treatment group for safety population and safety – Extension Study Period subset. In addition, a listing will be provided showing the CTCAE results for each patient by treatment group in the safety population.

The number and percentage of patients with CTCAE grade greater than or equal to 3 will be summarized by laboratory category, parameter, level, CTCAE grade and treatment group. The summary will be performed based on the data obtained during the Main Study Period or Extension Study Period, including all post-baseline scheduled, unscheduled and repeat visits. Only the most severe result will be counted a patient received the same tests in repeated visits.

The proportion of patients with Ig levels under LLN of the IgA, IgG and IgM will be summarized separately by visit and treatment group. Percentages are calculated by using the number of patients who have Ig levels at each visit as the denominator.

All hematology, clinical chemistry, urinalysis, and immunoglobulin data will be listed, and will include high and low flags to show if a value was outside the normal range.

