**APPENDIX 2: Table of CTCAE Terms and Grades**

CTCAE Term	Laboratory Parameter	Level	Grade 1	Grade 2	Grade 3	Grade 4
Anemia	Hemoglobin	Low	<LLN - 10.0 g/dL; <LLN - 100 g/L	<10.0 - 8.0 g/dL; <100 - 80g/L	<8.0 g/dL; <80 g/L;	-
Alanine aminotransferase increased	Alanine Aminotransferase (ALT)	High	>ULN - 3.0 x ULN	>3.0 - 5.0 x ULN	>5.0 - 20.0 x ULN	>20.0 x ULN
Alkaline phosphatase increased	Alkaline phosphatase	High	>ULN - 2.5 x ULN	>2.5 - 5.0 x ULN	>5.0 - 20.0 x ULN	>20.0 x ULN
Aspartate aminotransferase increased	Aspartate Aminotransferase (AST)	High	>ULN - 3.0 x ULN	>3.0 - 5.0 x ULN	>5.0 - 20.0 x ULN	>20.0 x ULN
Blood bilirubin increased	Total Bilirubin	High	>ULN - 1.5 x ULN	>1.5 - 3.0 x ULN	>3.0 - 10.0 x ULN	>10.0 x ULN
Chronic kidney disease	Creatinine Clearance (Est by Weight)	Low	<LLN - 60 ml/min	<60 - 30 ml/min	<30 - 15 ml/min	<15 ml/min

CPK increased	Creatine Phosphokinase (CPK)	High	>ULN - 2.5 x ULN	>2.5 x ULN - 5 x ULN	>5 x ULN - 10 x ULN	>10 x ULN
Creatinine increased	Creatinine	High	>1 - 1.5 x baseline; >ULN - 1.5 x ULN	>1.5 - 3.0 x baseline; >1.5 - 3.0 x ULN	>3.0 baseline; >3.0 - 6.0 x ULN	>6.0 x ULN
GGT increased	Gamma Glutamyl Transferase	High	>ULN - 2.5 x ULN	>2.5 - 5.0 x ULN	>5.0 - 20.0 x ULN	>20.0 x ULN
Hemoglobin increased	Hemoglobin	High	Increase in >0 - 2 gm/dL above ULN or above baseline if baseline is above ULN	Increase in >2 - 4 gm/dL above ULN or above baseline if baseline is above ULN	Increase in >4 gm/dL above ULN or above baseline if baseline is above ULN	-
Hypercalcemia	Calcium	High	>ULN - 11.5 mg/dL; >ULN - 2.9 mmol/L	>11.5 - 12.5 mg/dL; >2.9 - 3.1 mmol/L	>12.5 - 13.5 mg/dL; >3.1 - 3.4 mmol/L	>13.5 mg/dL; >3.4 mmol/L
Hyperkalemia	Potassium	High	>ULN - 5.5 mmol/L	>5.5 - 6.0 mmol/L	>6.0 - 7.0 mmol/L	>7.0 mmol/L

Hypernatremia	Sodium	High	>ULN - 150 mmol/L	>150 - 155 mmol/L	>155 - 160 mmol/L;	>160 mmol/L
Hypoalbuminemia	Albumin	Low	<LLN - 3 g/dL; <LLN - 30 g/L	<3 - 2 g/dL; <30 - 20 g/L	<2 g/dL; <20 g/L	-
Hypocalcemia	Calcium	Low	<LLN - 8.0 mg/dL; <LLN - 2.0 mmol/L	<8.0 - 7.0 mg/dL; <2.0 - 1.75 mmol/L	<7.0 - 6.0 mg/dL; <1.75 - 1.5 mmol/L	<6.0 mg/dL; <1.5 mmol/L
Hypoglycemia	Glucose	Low	<LLN - 55 mg/dL; <LLN - 3.0 mmol/L	<55 - 40 mg/dL; <3.0 - 2.2 mmol/L	<40 - 30 mg/dL; <2.2 - 1.7 mmol/L	<30 mg/dL; <1.7 mmol/L
Hypokalemia	Potassium	Low	<LLN - 3.0 mmol/L	<LLN - 3.0 mmol/L	<3.0 - 2.5 mmol/L	<2.5 mmol/L
Hyponatremia	Sodium	Low	<LLN - 130 mmol/L		<130 - 120 mmol/L	<120 mmol/L

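### Hypokalaemia Grades 1 and 2 share one numeric range, and the laboratory grade tables have no baseline grade, so persisting abnormalities are counted with new ones

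*SAP*

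**What the plan says.** SAP 13.2 (Clinical Laboratory Evaluations) states that "grading will be applied to post-baseline values for all numeric parameters where possible according to CTCAE v 4.0". For definitions that mix a number with a clinical judgement, "Grades which are part numeric and part clinical input will be assigned based on the numeric portion only". Appendix 2 supplies the ranges. The row at issue reads "Hypokalemia Potassium Low <LLN - 3.0 mmol/L <LLN - 3.0 mmol/L <3.0 - 2.5 mmol/L <2.5 mmol/L".

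Two tables use the grades:
- **By visit:** "The number and percentage of patients with a result for each grade will be summarized by CTCAE term, visit, and treatment group".
- **Grade 3 or higher:** covers the Main Study or Extension Period, "including all post-baseline scheduled, unscheduled and repeat visits". It adds that "Only the most severe result will be counted a patient received the same tests in repeated visits".

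For non-numeric urinalysis the same section plans a shift table: "The number and percentage of patients within each category will be displayed for baseline and for each post-baseline visit". No such display is described for the numeric grades. SAP 13.2 does keep actual values and change from baseline for continuous parameters, and high and low flags in the listings.

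SAP 5.5 defines baseline as the last non-missing value before the first infusion and treats every visit after that date as post-baseline.

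**The concern.** A grading rule should give each laboratory value exactly one grade. Part of the potassium scale gets two, so two programmers could both follow the SAP and produce different Grade 1 and Grade 2 counts.

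The second issue is what the tables can show. Without a baseline grade or a worsening condition, a patient who entered with an abnormality and stayed in the same range is indistinguishable from one who developed it on study drug. The rest of the plan avoids this. ECG (SAP 13.4) and physical examination (SAP 13.6) have shift tables, as does non-numeric urinalysis. Protocol 6.5.10.1 records a laboratory abnormality as an adverse event only if it is new or has worsened from baseline. The graded numeric laboratory results are the exception.

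What is at stake is the reading of the descriptive laboratory safety tables. No primary endpoint or similarity decision depends on them.

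**Working it through.** The documents give no figure to reproduce, so the check applies the rules as written.

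**1. Potassium row.** Inputs: Appendix 2 ranges and the numeric-part rule. Grades 1 and 2 are both "<LLN - 3.0 mmol/L", Grade 3 is 2.5 to below 3.0, and Grade 4 is below 2.5. The LLN is not in the documents, so 3.3, 3.5 and 3.6 mmol/L are assumed.

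| Potassium (mmol/L) | LLN 3.3 | LLN 3.5 | LLN 3.6 |
|---|---|---|---|
| 3.4 | none | 1 and 2 | 1 and 2 |
| 3.2 | 1 and 2 | 1 and 2 | 1 and 2 |
| 3.0 | 1 and 2 | 1 and 2 | 1 and 2 |
| 2.9 | 3 | 3 | 3 |
| 2.5 | 3 | 3 | 3 |
| 2.4 | 4 | 4 | 4 |

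The overlap runs from 3.0 up to whatever LLN applies and stops at Grade 3. The most-severe rule chooses among results from repeated visits in the Grade 3 or higher table. It does not choose between two grades met by one result. Of the 23 rows in Appendix 2, this is the only one with two identical ranges.

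**2. Worst grade that entry allows.** Inputs: Protocol 4.1.1, inclusion criteria 7 and 8, set against Appendix 2.

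| Parameter | Worst value allowed at Screening | Grade |
|---|---|---|
| Haemoglobin | 8.0 g/dL | 2 |
| Total bilirubin | just under 2 × ULN | 2 |
| ALT, AST | just under 2.5 × ULN | 1 |
| Neutrophils | 1.5 × 10⁹/L | 1, if below LLN |
| Platelets | 75 × 10⁹/L | 1, if below LLN |
| White cells | 3.5 × 10⁹/L | 1, if below LLN |

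Grade 3 is therefore excluded at the screening test for all of these. Lymphocytes, GGT, CPK, alkaline phosphatase, albumin, calcium, potassium, sodium and glucose have no laboratory entry limit, so Grade 3 or higher at entry is not excluded for them.

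**3. Following two patients through the tables.** Haemoglobin 9 g/dL at baseline and at every later test falls in the 8.0 to below 10.0 range. It counts as Grade 2 at each post-baseline visit and never reaches the Grade 3 or higher table. A lymphocyte count of 400/mm³ throughout lies between 200 and 500. It counts as Grade 3 at each visit and enters the Grade 3 or higher table, although nothing changed.

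**4. Extension Period.** SAP 5.5 sets one baseline, before the first infusion, so every Extension visit is post-baseline. Extension Week 0 samples are taken before the third-course infusion (Protocol Table 9), and nothing in SAP 13.2 leaves them out of the Extension tables. SAP 5.7 displays groups switched from Rituxan and from MabThera. The laboratory criteria for a further course cover neutrophils, platelets, AST or ALT, and IgG, but not lymphocytes. A Grade 3 lymphocyte count that arose on a reference product and persisted could thus be tabulated under a switched group, even from a sample drawn before the switch.

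**The case against.** The strongest reply is that these tables do what they say. They count patients with a result in each grade and do not claim treatment-emergent toxicity. Attribution belongs to adverse-event reporting, where an event must be new or worsened (SAP 13.1) and a stable condition present at screening is not reported (Protocol 6.5.10.3). Baseline-referenced information is already planned through change from baseline. The row for raised haemoglobin also adjusts for an abnormal baseline.

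Most of this stands. A reader might infer that the tables misgrade patients. They do not: outside the potassium overlap each value receives the grade its number earns, and inside it the grade is undetermined rather than shown to be wrong. What survives is narrower. Summaries of change from baseline do not show how many individual patients worsened in grade, and the adjusted haemoglobin row does not help the others.

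On potassium, it can be argued that SAP 13.2 settles the matter because it withholds grades that need clinical input only, which would leave Grade 1. That reading is reasonable but unstated. Appendix 2 prints a numeric range for Grade 2, and the numeric-part rule says to use it.

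A reader might also take the blank Grade 2 cell for hyponatraemia as a second error. It is not: Grade 1 runs down to 130 mmol/L and Grade 3 begins below 130, so no value has two grades.

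**Conclusion.** The point holds as a minor one, in two parts.

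- **Potassium:** Grade 1 and Grade 2 by-visit counts cannot be determined from the SAP for one row of 23. Hypokalaemia Grades 3 and 4 and the Grade 3 or higher table are unaffected.
- **Baseline:** abnormalities that persist from entry are counted in both tables. For haemoglobin and bilirubin, persistence of the worst grade allowed at Screening contributes at most Grade 2. For parameters without an entry limit, such as lymphocytes and GGT, it can reach Grade 3 or higher.

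In the Main Study Period randomisation balances entry abnormalities in expectation, so the effect is higher absolute counts in every arm. A reader might infer a bias for or against CT-P10, and the documents do not support that. The Extension tables need more care, because carried-over abnormalities can sit under a treatment label that was not in force when they arose. That part rests on reading the first infusion in SAP 5.5 as the first of the whole study.

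The number of patients affected is unknown, since entry distributions and the laboratory's LLNs are not given. Nor do the documents rank these tables as the main laboratory safety comparison. Protocol 7.8.4.3 plans visit summaries, change from baseline and listings.

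**What to change.** - **Appendix 2:** assign the shared potassium range to a single grade, either Grade 1 or one combined Grade 1/2 category, and say so in the row.
- **SAP 13.2, Main Study:** grade the baseline value. Add a table of baseline grade by worst post-baseline grade, or a count of patients whose grade worsened from baseline. Do the same for Grade 3 or higher.
- **SAP 13.2, Extension:** use the graded pre-dose Extension Week 0 value as the reference for these displays.

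The existing by-visit table can stay. The cost is one appendix row, a few sentences in the SAP, and modest extra programming and tables. All the values needed are already collected.
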